16. APPENDICES

SCHEDULE OF ASSESSMENTS

Table 1. Study plan
(ALL THESE PROCEDURES SHOULD BE CARRIED OUT IN THE FRAMEWORK OF ROUTINE PRACTICE OF THE HEALTH CARE INSTITUTIONS)

Procedure / days	Study according to the Protocol No. COVID dated March 30, 2020				
	Day 1	Daily (up to discharge ^{***})	Day 3, 5, 7, 11	Day 15±1	Day 29±3 or any other last day ^{****} of the study
Enrolment criteria	X				
Withdrawal criteria		X	X	X	X
Informed consent, enrolment	X				
Polyoxidonium	10 doses: days 1, 2, 3, 5, 7, 9, 11, 13, 15, 17				
History	X				
Clinical signs and symptoms, physical examination¹	X	X	X	X	X
Nasopharyngeal and/or oropharyngeal smear	X		X	X	X
Haematology²	X**		X	X	X
Blood chemistry³	X**		X	X	X
CRP	X**		X	X	X
Urinalysis⁴	X**		X	X	X
Bacteriological inoculation of sputum	If necessary				
Chest X-ray/ CT*	If indicated				
ECG*	If indicated				
SpO₂⁵	X	X	X	X	X
Evaluation of need for oxygenation, including mechanical ventilation	X	X	X	X	X
Assessment of the treatment efficacy⁶	X	X	X	X	X
Assessment of safety	X	X	X	X	X
NEWS Score	X	X	X	X	X
SOFA Score	X	X	X	X	X
Clinical status by WHO scale	At admission	X	X	X	X

Notes to Table 1

*- including at admission, before enrolment

** - results of the previous laboratory investigations within 48 hours before enrolment can be used

*** - visits to the clinic are preferred after discharge, but the quarantine or other reasonable factors can limit this opportunity. The visits could be performed in a form of phone call or with other remote communication technologies. Some data will not be collected by obvious reasons.

**** - in case of the patient withdrawal (see the withdrawal criteria)

1 – Clinical signs and symptoms

Weakness, fatigue, cough, shortness of breath, stuffiness in the chest, myalgia, headaches, haemoptysis, palpitations, nasopharyngeal symptoms, diarrhoea, nausea, vomiting; physical

examination: heart rate, blood pressure, respiratory rate, body temperature

2 – Haematology

Red blood cells, haematocrit, white blood cells, platelets, neutrophils, eosinophils, basophils, monocytes, lymphocytes

3 - Blood chemistry

Urea, creatinine, Na⁺, K⁺, bilirubin, glucose, ALT, AST, albumin, pH, bicarbonates, lactate, coagulogram with prothrombin time, coagulogram with international normalized ratio and activated partial thromboplastin time, CRP

If indicated: PaO₂, FiO₂, PaCO₂

4 – Urinalysis

According to routine practice of the centre

5 - SpO₂

With qualitative assessment of oxygenation, including mechanical ventilation

6 – Assessment of the treatment efficacy

The maximal treatment effect, the treatment effect evaluated by the doctor

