4. STUDY DESIGN

4.1. Primary and Secondary Outcomes

According to the aim and objectives of this study, safety and efficacy of Polyoxidonium®, lyophilizate for solution for injections and topical application, 6 mg (NPO Petrovax Pharm LLC, Russia) will be evaluated in hospitalized patients with coronavirus disease (COVID-19).

Efficacy outcomes

Primary efficacy outcome

Subject clinical status using the WHO 7-point ordinal scale on day 15 as compared to baseline.

1. Not hospitalized, no limitations on activities.
2. Not hospitalized, limitation on activities.
3. Hospitalized, not requiring supplemental oxygen.
4. Hospitalized, requiring supplemental oxygen.
5. Hospitalized, on non-invasive ventilation or high flow oxygen devices.
6. Hospitalized, on invasive mechanical ventilation or ECMO.
7. Death.

Secondary efficacy outcomes

Clinical severity assessed by scales

1. Subject clinical status using the WHO 7-point ordinal scale

- Time to improvement of each parameter of the primary scale from admission.

- Subject clinical status at days 3, 5, 8, 11, and 29.
 - Average change in the clinical status at days 3, 5, 8, 11, 15, and 29 as compared to baseline.
2. *The NEWS Score (National Early Warning Score) describes the vital signs (pulse rate, breathing rate, temperature, blood pressure etc.) and its deviation from the reference ranges):* is evaluated daily and on day 15.
- The time to discharge or to a NEWS of ≤ 2 and maintained for 24 hours, whichever occurs first.
 - Change from baseline to days 3, 5, 8, 11, 15, and 29 in NEWS.
3. *Oxygenation, including mechanical ventilation:*
- Change (day by day) in the need for oxygenation in the first 28 days (up to day 29).
4. *Hospitalization*
- Duration of hospitalization (days).
5. *Mortality (date, cause)*
- 28-day mortality.
6. *SOFA scale (evaluation of organ failure associated with sepsis):* is evaluated daily and on day 15.
- Change from baseline to days 3, 5, 8, 11, 15, and 29 in SOFA.

Safety outcomes

Safety outcomes

- Cumulative incidence of serious adverse events/reactions (SAEs, SARs)
- Cumulative incidence of adverse events/reaction (AEs, ARs)
- Permanent or temporary discontinuation of infusions/injections (by any cause)
- Clinically significant changes in the levels of leukocytes, haemoglobin, platelets, creatinine, glucose, total bilirubin, ALT, AST, CRP, and other parameters.

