6. STUDY PLAN

6.1 Schedule of the study visits and procedures

The study will be conducted in the clinical centre during hospitalization and outpatient visits of patients who were discharged by their attending physician according to routine clinical

practice.

The study will include the following periods:

Treatment period (17 days in total, days 1...17) with administration of the investigational product (intravenous injections for 3 days, then intramuscular injections for 14 days), assessment of the clinical status, recording of AEs.

Follow-up period (days 18...29±3)

Additional visits can be performed if judged necessary by the study doctor. The study doctor will define the scope of assessments and procedures for the additional visits individually, based on the patient's needs.

The Early Termination Visit is performed if the patient is withdrawn from the study. The scope of activities and procedures carried out at the visit is similar to the activities and procedures carried out at the visit on Day 29.

Schedule of the study procedures is included in the Appendix 1.

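### 28-day mortality runs to Day 29, but the plan requires no vital-status check on or after Day 29 and has no analysis rule for patients withdrawn or last seen on Day 26 to 28

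*Combined protocol and SAP*

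**What the plan says.** Section 4.1 lists mortality among the secondary efficacy outcomes under "Mortality (date, cause"), with "28-day mortality" as the measure. The synopsis and section 7.1 repeat it. None of them defines the denominator or the source of vital status. Day 1 is enrolment (6.2), and the oxygenation outcome in 4.1 shows how days are counted: "in the first 28 days (up to day 29").

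Section 6.1 gives the schedule as "Follow-up period (days 18...29±3"), and Table 1 heads its last column "Day 29±3 or any other last day". The footnote explains the alternative: "in case of the patient withdrawal (see the withdrawal criteria"). Section 6.1 adds: "The Early Termination Visit is performed if the patient is withdrawn from the study". Its content is meant to resemble that of the Day 29 assessment. Table 1 has no row for vital status; death appears only as category 7 of the WHO scale.

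Three other sections bear on the analysis:
- 13.4 has the eCRF completed only as far as withdrawal.
- 9.4 neither replaces missing data nor takes them into account.
- 9.6 and 9.7.2 make all enrolled patients the main efficacy population.

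Kaplan-Meier is planned for time-to-event data (9.1, 9.7.2.2), but mortality is not named as one of these.

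**The concern.** A mortality figure at a fixed day needs vital status known through that day, or a rule for patients in whom it is not known. The plan guarantees neither. A compliant last visit can come up to three days before Day 29, and a compliant early termination visit can come weeks before it, with no later contact scheduled.

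The withdrawn patients are the more worrying group. Two withdrawal criteria in 5.3 are an adverse event whose work-up or treatment disturbs the study procedures, and a need for additional treatment that could affect the results or the patient's safety. Both can mark a deteriorating patient, so follow-up may stop in the patients at highest risk. Withdrawn patients are not replaced (5.5). At stake is whether the reported proportion really describes 28 days in all enrolled patients.

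**Working it through.** The plan gives no mortality rate, dropout rate or sample size calculation, so there is no figure to reproduce. N = 50 is the stated minimum. All mortality rates and counts below are assumptions.

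**1. Days.** 29 − 1 = 28, so 28 days of follow-up end on Day 29. The window runs from 29 − 3 = Day 26 to 29 + 3 = Day 32. A patient last seen on Day 26 has 25 days observed and 3 not observed. A patient seen on Day 29 to 32 is fully ascertained, and the recorded date of death allows deaths after Day 29 to be left out.

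**2. Window effect, upper limit.** Suppose all 50 patients were last seen on Day 26, later deaths went unrecorded, and the hazard was constant. For true 28-day mortality m, the share seen by Day 26 is 1 − (1 − m)^(25/28), and the expected number of missed deaths is 50 × (m − share seen).

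| Assumed m | Seen by Day 26 | Expected deaths missed in 50 |
|---|---|---|
| 5% | 4.5% | 0.3 |
| 10% | 9.0% | 0.5 |
| 20% | 18.1% | 1.0 |

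For m = 20%: 1 − 0.80^(25/28) = 0.1806, and 50 × (0.20 − 0.1806) = 0.97.

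**3. Withdrawal effect.** Take 5 observed deaths among 50 enrolled, with u withdrawn patients of unknown Day 29 status.

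| u | Unknowns counted alive | Unknowns dropped | Unknowns all dead |
|---|---|---|---|
| 2 | 5/50 = 10% | 5/48 = 10.4% | 7/50 = 14% |
| 5 | 5/50 = 10% | 5/45 = 11.1% | 10/50 = 20% |
| 10 | 5/50 = 10% | 5/40 = 12.5% | 15/50 = 30% |

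**4. Direction.** Counting unknowns as alive can only understate mortality. Dropping them can err either way. With u = 5 the complete-case figure is 11.1%. If none of the five died, the truth is 10% and 11.1% is too high. If one died, the truth is 6/50 = 12% and 11.1% is too low.

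**5. Which rule applies.** Section 9.4 points towards dropping, 9.6 towards keeping everyone, and 9.1 could mean censoring. Section 11.8 adds a second route to exclusion: it classes a missed visit as a significant deviation and removes such patients from the efficacy analysis. Nothing says which of these governs mortality.

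**6. With Day 29 status known for all.** The bounds collapse to one value: 5/50 = 10.0%, exact 95% CI 3.3% to 21.8%.

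**The case against.** Several provisions narrow the gap:
- Patients who only stop the drug should stay in the study for endpoint measurements if possible (5.4).
- Consent counts as withdrawn only when the patient no longer authorizes efforts to obtain outcome data, and attempts to contact patients lost to follow-up are required (4.5).
- Patients withdrawn for an AE or SAE are followed to resolution or stabilization (5.3, 5.6).
- Remote visits are allowed (6.2, Table 1).
- A death is an SAE, and a site that learns of one after the study must report it (8.3.6).
- Inpatients are assessed daily until discharge, so an in-hospital death on Day 27 would hardly go unseen.

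These points stand, and they are why deaths *may* be missed rather than *are* missed. They also confine the window problem largely to discharged patients last seen on Day 26 to 28. None of them sets Day 29 as a target, however. Follow-up to stabilization can end before Day 29. SAE reporting after the study is passive and is not linked to the efficacy dataset.

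A reader might infer three stronger things, which the documents do not support:
- *That mortality is read from the last visit, so a patient seen alive on Day 26 counts as a 28-day survivor.* No section says so; deaths are to be dated, and Kaplan-Meier, if applied, would censor that patient.
- *That the error always favours the product.* This holds only if unknowns are counted as alive (step 4). The study also has a single group, so there is no comparator against which to bias.
- *That early termination data are tabulated as Day 29.* They share a column in Table 1, but 6.1 names a separate visit and no tabulation rule is given.

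**Conclusion.** The gap is real but limited. Following the plan as written can leave Day 29 vital status uncollected for withdrawn patients and for discharged patients seen on Day 26 to 28, and no rule says how they enter the 28-day mortality estimate.

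The window part is small: at most about one expected death in 50, under a constant hazard, an assumed 20% mortality and the extreme case that everyone is seen on Day 26. The withdrawal part is the material one. With assumed counts of 5 deaths in 50 and 5 unknown, the 10-point span of the bounds compares with a half-width of about 9 points ((21.8 − 3.3)/2) for the sampling interval. The actual size depends on how many patients withdraw and how many of those are traced, which the documents do not indicate. As this is a secondary endpoint in an uncontrolled study, the change is advisable and cheap; the gap does not undermine the study as a whole.

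**What to change.** - **Schedule (Table 1 and 6.1).** Add a vital-status item on Day 29 (+3 days, not earlier) for every enrolled patient, including those withdrawn or discharged, by phone or hospital record. Except patients who no longer authorize collection of outcome data, in line with 4.5. The ±3 window can stay for the other assessments.
- **Data capture (13.4).** Exempt this item from the eCRF stop at withdrawal. Record the date of death or the date last known alive. Label early termination data separately from Day 29.
- **Analysis (9.7.2.2).** Count deaths dated on or before Day 29. Estimate 28-day mortality by Kaplan-Meier in all enrolled patients, censoring at the date last known alive, and state that 9.4 and 11.8 do not remove anyone from this estimate. Report the number with unknown status and the best-case and worst-case bounds, because censoring at withdrawal may be informative.

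The cost is at most one extra remote contact per patient, one added date field, and a narrower window for one item. Day 32 stays the upper limit, so the maximum participation in 4.4 is unchanged. Patients who refuse further data collection will still be unknown, and the bounds show how much they matter.
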